The purpose of this Aim is to evaluate the feasibility of utilizing the 3DIZI technique to optimize BTX injections in patients with focal spasticity. Clinical and quantitative assessments of spastic biceps of stroke subjects between 3DIZI-guided and standard injections at baseline, 3 weeks, and 3 months post-injections will be compared. The clinical effect of BTX injection usually reaches to its peak at about 3 weeks, and lasts for 3 months. It is expected that outcomes (clinical and quantitative measures) will be better in the 3DIZI-guided injection group than in the standard injection group at 3 weeks and 3 months post-injection. Both groups are expected to have comparable baseline measures.

Patient selection: We plan to recruit 16 post-stroke subjects who are currently receiving BTX injections for their spastic biceps every 3 months at TIRR Outpatient Spasticity Management Clinic into two groups: the IZ-guided injection group and the standard injection group (Please see human subject protect section for characteristics of stroke patients).

BTX injections: Both groups of patients will be recruited prior to their routine BTX injection schedule. Baseline assessment (screening, clinical assessment, and quantitative assessment) will be performed 1 day prior to injection. Stroke patients with elbow flexors spasticity of modified Ashworth scale (MAS) of 2 or 3 will be recruited. The number of MAS (2s or 3s) will be matched between two groups. The type of BTX (we will choose botox because it is most commonly used in US) and amount of BTX (usually 100 units) and dilutions (usually double dilution) will be consistent between two groups. These parameters (type, dose, dilution) are standard of care at TIRR Spasticity Management Clinic. For standard injection procedures, target muscles will be visualized under ultrasound imaging which is operated by an experienced and dedicated technician. Position of needle tip within the target muscle is visualized prior to

[figure not shown]

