These measures will be made at baseline, 3 weeks and 3 months post-injection. Two-way ANOVA with factors of GROUP (x2) and TIME (x3) will be performed on reflex torque values. It is anticipated that MAS scores, reflex torque values are comparable at baseline, but will be significantly reduced at 3 weeks and 3 months for both groups. Reduction is expected to be significantly more in the IZ-guided injection group than in the standard group. We do anticipate great reduction in elbow flexor spasticity as quantified by reflex-torque measurement after the IZ-guided injection. However, MAS scores are not as reliable in general (Craven and Morris 2010), and could be influenced by other elbow flexors.

Pitfalls: If other elbow flexors are required to be injected but may not be consistent across subjects, it is unethical not to inject (treat) these muscles. Assessment of biceps spasticity may be influenced and thus MAS scores may not accurately reflect the spasticity reduction effect from biceps muscles alone. Efforts will be made to balance treatment plans between groups in the recruitment process.

Limitation: Eight patients and 16 patients (8 patients per group) are proposed for Exp 1 and Exp 2 respectively. We expect that 8 subjects in each group should be sufficient to detect difference should it exist, according a recent study (Lapatki et al. 2011). These estimated numbers fit in the scope of work of this 2-year exploratory project. A power analysis will be performed at the completion of this project to decide whether or how many more subjects will be needed for a future study. Full-time biostatisticians are available at both UH and TIRR (see Facilities and Other Resources section) for statistical analysis support.

The implementation of the 3DIZI technique currently proposed in the proposal is relatively complicated, because the main purpose of this project is to evaluate the performance of the proposed 3DIZI and examine the feasibility of its application to clinic. As the next step, we plan to simplify the implementation of the 3DIZI technique to make it appropriate for clinic use.

Specimens:

No specimens will be collected

5. Human Subjects

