- any condition that, in the judgment of a physician, would prevent the person from participating. Efforts will be made to match a variety of measures between two groups, such as age, gender, time from stroke, spasticity in other elbow flexors (e.g., brachioradialis), and injection sites. Given the volume of patients in TIRR Spasticity Management Clinic, we are confident that we can achieve this goal.

Potential subject populations and recruitment: Subjects will be recruited from TIRR outpatient clinic.

6. Data Collection and Analysis

A desktop computer will be used for data acquisition and processing. Data will be saved for off-line analysis using customized MatLab software and Statistica software.

Experiment 1: This is a validation study. Detailed information has been provided above.

Experiment 2: These measures will be made at baseline, 3 weeks and 3 months post-injection. Two-way ANOVA with factors of GROUP (x2) and TIME (x3) will be performed on reflex torque values. It is anticipated that MAS scores, reflex torque values are comparable at baseline, but will be significantly reduced at 3 weeks and 3 months for both groups. Reduction is expected to be significantly more in the IZ-guided injection group than in the standard group. We do anticipate great reduction in elbow flexor spasticity as quantified by reflex-torque measurement after the IZ-guided injection. However, MAS scores are not as reliable in general (Craven and Morris 2010), and could be influenced by other elbow flexors.

Demographic data will be analyzed descriptively. Personal information will be de-identified.

7. Potential Risks/Discomforts:

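### Pre-injection reflex torque enters the ANOVA as an outcome level and not as a covariate, which costs power at 8 per group unless the visits are highly correlated

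*Combined protocol and SAP*

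**What the plan says.** The analysis sentence appears in Section 4 (Experiment 2, treatment outcome evaluation) and again in Section 6: "Two-way ANOVA with factors of GROUP (x2) and TIME (x3) will be performed on reflex torque values". Both places give the visits: "These measures will be made at baseline, 3 weeks and 3 months post-injection". The paragraph on BTX injections in Section 4 fixes the first of them: "Baseline assessment (screening, clinical assessment, and quantitative assessment) will be performed 1 day prior to injection". So one of the three TIME levels precedes any treatment.

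The hypothesis is about change: "Reduction is expected to be significantly more in the IZ-guided injection group than in the standard group". The plan does not say whether GROUP, GROUP x TIME or a contrast tests it. On baseline it says only: "Both groups are expected to have comparable baseline measures". Groups are to be matched on MAS grade (Section 4) and, as far as possible, on age, gender, time from stroke, spasticity in other elbow flexors and injection sites (Section 5). Reflex torque is not on the list, and no randomisation is described. The stretch end point is set relative to each patient's resting elbow angle to allow for baseline differences. That is a measurement step, not a statistical adjustment.

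On size: "Eight patients and 16 patients (8 patients per group) are proposed for Exp 1 and Exp 2 respectively", supported by "We expect that 8 subjects in each group should be sufficient to detect difference should it exist, according a recent study". No alpha, power, effect size, SD or correlation is given.

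**The concern.** Every patient has a reflex torque value before guidance can have acted. That value is most useful as a predictor of later torque, yet the stated model treats it as another outcome.

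- If GROUP is the test, a visit with no possible effect is averaged with two visits that may have one.
- If GROUP x TIME or a change contrast is the test, the whole baseline value is subtracted. This adds noise unless baseline and follow-up are highly correlated.

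Adding a patient term to the ANOVA cures neither problem. With 16 patients, and reflex torque the only outcome with a stated test, the lost precision matters. It also matters later: "A power analysis will be performed at the completion of this project", and that calculation will draw on the effect estimate and residual variance from this analysis.

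**Working it through.** **The plan's own figure.** Without alpha, power, effect size or SD, 8 per group can be neither reproduced nor refuted. For orientation, a single-visit two-sample t test with 8 per group has 79.7% power at a 1.5 SD difference (two-sided 5%).

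**Inputs.** From the documents: 8 per group, three visits, no effect possible at baseline, equal expected baselines. Assumed: SD 1 at each visit, the same correlation r between every pair of visits, benefit d (in SD) at both post-injection visits, two-sided 5%, and a correct within-patient error term for every test.

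**Variance per patient, and effect, for each analysis**
- ANCOVA of the post-injection mean on baseline: (1+r)/2 − r²; effect d; 13 df.
- Post-injection mean minus baseline: (1+r)/2 + 1 − 2r; effect d; 14 df.
- GROUP over three visits: (1+2r)/3; effect 2d/3; 14 df.
- GROUP x TIME: the group differences 0, d, d deviate from their mean by −2d/3, d/3, d/3, with sum of squares 2d²/3. The noncentrality is (8/2)(2d²/3)/(1−r), on 2 and 28 df.

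The change variance minus the ANCOVA variance is 1 − 2r + r² = (1−r)², which is never negative.

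**At r = 0.5, d = 1** (standard error = √(variance × 2/8))
- ANCOVA: variance 0.75 − 0.25 = 0.50; SE 0.354; ratio 2.83, slightly reduced by chance baseline imbalance; power 71.2%.
- Change: variance 0.75 + 1 − 1 = 0.75; SE 0.433; ratio 2.31; power 57.5%.
- GROUP x TIME: noncentrality 4 × 0.667/0.5 = 5.33; power 48.6%.
- GROUP: effect 0.667; variance 0.667; SE 0.408; ratio 1.63; power 33.1%.

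Simulation agrees: about 72, 58, 49 and 33%.

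**Power (%) over the correlation, d = 1**

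| r | ANCOVA | Change | GROUP x TIME | GROUP | ANCOVA minus change |
|---|---|---|---|---|---|
| 0.3 | 66.4 | 44.4 | 36.2 | 39.8 | 22 |
| 0.5 | 71.2 | 57.5 | 48.6 | 33.1 | 14 |
| 0.7 | 84.2 | 79.2 | 71.6 | 28.5 | 5 |
| 0.8 | 93.4 | 92.4 | 88.2 | 26.6 | 1 |

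**Over the effect size, r = 0.5.** ANCOVA minus change is 12 points at 0.8 SD, 12 at 1.2 SD and 7 at 1.5 SD.

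**Benefit that wanes (simulated)**
- Half the benefit left at 3 months, r = 0.5: averaged ANCOVA 48%, GROUP x TIME 38%, GROUP 21%.
- The same at r = 0.8: ANCOVA 75%, GROUP x TIME 77%.
- No benefit left at 3 months, r = 0.5: averaged ANCOVA 24%, GROUP x TIME 49%, ANCOVA at 3 weeks alone 54%.

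**Baseline imbalance.** A chance difference δ shifts the GROUP estimate by (1+2r)/3 × δ and the change contrast by −(1−r) × δ. At r = 0.5 these are +0.67δ and −0.50δ. ANCOVA shifts by 0 when expected baselines are equal. The difference has SE √(2/8) = 0.5 SD, so under simple chance allocation it exceeds 0.5 SD in about 32% of trials. Matching would lower that to the extent that the matched factors predict reflex torque.

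If the groups instead differ stably by δ, change shifts by 0 and ANCOVA by (1−r)δ. With δ = 0.5 SD and r = 0.5 that is 0.25 SD. Simulated type I error is then about 9% for ANCOVA and 5% for change. If the guided group starts 0.5 SD higher and the true benefit is 1 SD, ANCOVA has about 45% power and change 57%.

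**The case against.** The strongest objection is that the groups are matched and no randomisation is described. If they differ systematically at baseline, ANCOVA can be biased where change from baseline is not. A reader might infer that adjustment removes any baseline imbalance. It does so only if expected baselines are equal. The plan makes that assumption but does not secure it by design. This objection stands and shapes the fix.

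A reader might also infer a loss of up to 38 points (71.2 − 33.1). That applies only if the three-visit GROUP effect is the test. The plan never says so, and its hypothesis of greater reduction points to GROUP x TIME. Nor is the 23-point gap to GROUP x TIME (71.2 − 48.6) all due to baseline handling: about 9 points (57.5 − 48.6) come from replacing a 2-df test with one averaged contrast, leaving about 14 for the covariate. Even that figure needs an effect near 1 SD and a correlation near 0.5, and the documents give neither.

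The averaged contrast is not always the better one. The protocol expects the toxin effect to peak at about 3 weeks, so a waning difference is plausible, although it predicts benefit at both visits. If the benefit is confined to 3 weeks, GROUP x TIME wins.

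Finally, Experiment 2 is an exploratory feasibility study, and a GROUP x TIME ANOVA with a proper within-patient error term is a valid test of differential change. That limits the weight of the point. It does not remove it, because the protocol also calls 8 per group sufficient to detect a difference.

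**Conclusion.** The point holds as one of efficiency and specification. Baseline reflex torque is an outcome level, is never a covariate, and no effect in the stated model uses it well at moderate correlation. At an assumed 1 SD benefit at both visits, the covariate alone gains about 22, 14, 5 and 1 points over the change contrast at correlations of 0.3, 0.5, 0.7 and 0.8. At correlation 0.5 and 1.5 SD it gains about 7.

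These sizes rest on equal variances, equal correlations, a sustained benefit and equal expected baselines. The documents do not support the stronger readings that the ANOVA is invalid, that the loss is large whatever the correlation, or that ANCOVA is safe however the groups were formed. The change is worth making because it is nearly free and makes the plan name its group comparison.

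**What to change.** In Sections 4 and 6, replace the three-level ANOVA as the group comparison with text such as:

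> Reflex torque at 3 weeks and 3 months is analysed in a model with GROUP, TIME (2 levels), GROUP x TIME, baseline reflex torque as a covariate and patient as a random effect. The guidance effect is the adjusted GROUP difference averaged over the two visits, with its 95% CI. The adjusted difference at each visit is shown beside it. Allocation is by matching, so this estimate assumes equal expected baselines. The change-from-baseline contrast is reported as a sensitivity analysis.

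Keep the three-level TIME ANOVA to describe change within groups.

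The cost is a few sentences and one error degree of freedom (14 to 13, already in the power figures). No new data, visits or patients are needed. The downsides are little gain if the correlation is 0.8 or more, dilution of the averaged difference if benefit is confined to 3 weeks (hence the by-visit results), and possible bias if the matched groups differ systematically at baseline (hence the sensitivity analysis).

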injection. Ultrasound guidance can help ensure depth of needle tip location, i.e., to make sure the needle tip is within the muscle, but it is not able to tell where it is located with reference to the IZs of the entire muscle. However, in the IZ-guided injection technique, IZ location obtained using the 3DIZ will be first marked over the skin surface of the muscle and the depth of the IZ will be also provided. The 3DIZ as described in Aim 1 will be applied to the IZ-guided injection group 1 day prior to scheduled injection. The surface location and depth information of the IZ will be used to guide where the needle tip needs to go. Currently, patients commonly receive 1 to 2 injection sites, occasionally 3 sites for biceps muscles. To standardize the procedure, we will choose 2 sites for all patients.

Treatment outcome evaluation and comparison: Treatment outcomes include clinical assessment of spasticity (MAS scale, see Human Subject Protection section) and quantitative assessment. Standard physical therapy will be ordered to both groups as part of standard of care for patients after BTX injections to maximize the outcomes. For quantitative assessment, we will adopt the same protocol in our recent study which quantified elbow flexors spasticity by measuring reflex torque (Figure 6)(Bhadane et al. 2015).

Fig. 6: Experimental setting (upper) and representative data (lower).

Each subject will receive a total of 60 degrees of computer-controlled elbow extension stretching at different speeds. The stretch ends at 10 degrees beyond the resting angle of the elbow joint during standing to offset the baseline difference among subjects (Bhadane et al. 2015). From the angle-torque relations, reflex torque is obtained after subtracting passive torque at 5°/sec from those at 50°/sec or 100°/sec. reflex torque is considered to reflect neural component of muscle spasticity (Kamper et al. 2001; Kamper et al. 2003; Li et al. 2006). It is expected to be reduced with spasticity reduction after neuromuscular blockade by Botox.

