As mentioned above, it is a limitation in estimation of the number of subjects for each experiment. Eight patients and 16 patients (8 patients per group) are proposed for Exp 1 and Exp 2 respectively. We expect that 8 subjects in each group should be sufficient to detect difference should it exist, according a recent study (Lapatki et al. 2011). These estimated numbers fit in the scope of work of this 2-year exploratory project. A power analysis will be performed at the completion of this project to decide whether or how many more subjects will be needed for a future study. Full-time biostatisticians are available at both UH and TIRR (see Facilities and Other Resources section) for statistical analysis support.

Gender will be balanced

Inclusion and Exclusion Criteria:

Inclusion criteria for participation in the study will include:

- a history of not more than one stroke which occurred at least 6 months prior to study enrollment;
- elbow flexor spasticity rated at 2 or 3 on Modified Ashworth scale (MAS);
- receiving repeated botulinum toxin injection every 3-4 months;
- absence of excessive pain in the paretic upper limb;
- capacity to provide informed consent, with Mini-Mental State Examination (MMSE) must be 25 or higher;

The following modified Ashworth scale (MAS) will be used for spasticity assessment:

- 0 -No increase in muscle tone;
- 1 -Slight increase in muscle tone, manifested by a catch and release or by minimal resistance at the end of the range of motion when the affected part(s) is moved in flexion or extension;
- 1+ -Slight increase in muscle tone, manifested by a catch, followed by minimal resistance throughout the remainder (less than half) of the ROM;
- 2 -More marked increase in muscle tone through most of the ROM, but affected part(s) easily moved;
- 3 -Considerable increase in muscle tone, passive movement difficult;
- 4 -Affected part(s) rigid in flexion or extension.

Main exclusion criteria:

- recent botulinum toxin injection < 4 months;
- recent changes in antispastic medications <3 weeks (i.e., the antispastic medication regime is not stable);
- Changes in antispastic medications (such as baclofen, tizanidine, dantrolene etc) during the followup research visits. (NOTE: it is clinically rare for patients who receive repeated injections to change their antispastic medications);
- history of spinal cord injury or traumatic brain damage;
- history of serious medical illness such as cardiovascular or pulmonary complications;

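### The exclusion for a botulinum toxin injection within 4 months rules out the on-schedule 3-month patients that Experiment 2 says it will recruit

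*Combined protocol and SAP*

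**What the plan says.** The relevant statements are in two places in the combined protocol and SAP.

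Section 4, Experiment 2:
- Patient selection takes 16 post-stroke patients "currently receiving BTX injections for their spastic biceps every 3 months".
- BTX injections states: "Both groups of patients will be recruited prior to their routine BTX injection schedule".
- The same paragraph fixes the visit: "Baseline assessment (screening, clinical assessment, and quantitative assessment) will be performed 1 day prior to injection".
- The innervation-zone imaging "will be applied to the IZ-guided injection group 1 day prior to scheduled injection".

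Section 5, Human Subjects:
- There is one list for the whole study, introduced by "Inclusion criteria for participation in the study will include". It has no separate list or exemption for Experiment 2.
- Inclusion requires "receiving repeated botulinum toxin injection every 3-4 months".
- The first main exclusion is "recent botulinum toxin injection < 4 months".
- After the criteria, on group balance: "Efforts will be made to match a variety of measures between two groups, such as age, gender, time from stroke". Spasticity in other elbow flexors and injection sites are also named. Time since last injection is not.

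**The concern.** A patient treated on a 3-month cycle and assessed the day before the next injection has, by construction, been injected less than 4 months ago. Followed literally, the exclusion removes the people Experiment 2 is designed around. If it is ignored, every on-schedule enrolment breaches a written criterion.

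The meaning of baseline is also at stake. Experiment 2 has its last outcome visit 3 months after injection, and Section 6 expects reflex torque and MAS still to be reduced then. Under the Section 4 schedule, baseline is itself about 3 months after the previous injection, the same point in the cycle as that last visit. Under the Section 5 exclusion, baseline is at least 4 months after it. The change from baseline to 3 months therefore means different things under the two texts.

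If site staff settle the conflict patient by patient, time since last injection could differ between two groups of only 8, and with it baseline MAS and reflex torque. Reflex torque is the measure in the GROUP by TIME ANOVA.

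**Working it through.** The plan gives no figure of its own to reproduce here, so the check is calendar arithmetic.

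**Inputs**
- Routine cycle: 3 months (Section 4, Patient selection); 3 to 4 months (Section 5, inclusion).
- Screening and baseline: 1 day before the injection (Section 4, BTX injections).
- Exclusion limit: less than 4 months since the last injection (Section 5).
- Assumption: a mean month of 365.25 / 12 = 30.44 days, checked against actual calendar dates.

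**Formulas**
- Days since last injection at baseline = cycle length − 1.
- Shortfall = 4-month limit − days at baseline.
- The limit is 4 × 30.44 = 121.75 days.

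| Routine cycle | Days at baseline | Shortfall to 121.75 days | Calendar range at baseline | Calendar shortfall |
|---|---|---|---|---|
| 3 months | 91.3 − 1 = 90.3 | 31.4 | 88 to 91 | 29 to 32 |
| 4 months | 121.75 − 1 = 120.75 | 1 | 119 to 122 | 1 |

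**Which day counts**
- Judged at the screening visit, every on-schedule patient in the 3-to-4-month inclusion range meets the exclusion.
- Judged on the injection day, the 3-month patient is still 121.75 − 91.3 = 30.4 days short. The exact 4-month patient sits at the limit and is not excluded. Everyone in between is.
- The protocol does not say which day applies.

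**Delay needed**
For a 3-month patient to pass at screening, the injection must fall at 121.75 + 1 = 122.75 days. That is 122.75 − 91.3 = 31.4 days late, or 31.4 / 91.3 = 34% beyond the cycle.

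**Other readings of the text**
- *The exclusion applies only to Experiment 1.* The list covers the whole study and makes no such distinction.
- *Recent means an injection outside the routine cycle.* This would remove the conflict, but the text does not say it. The next exclusion, on antispastic medication, uses the same form to mean elapsed time.
- *The routine injection is postponed.* No washout or postponement is described. Section 4 refers throughout to the routine or scheduled injection.

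**The case against.** The case on the other side accepts that the texts conflict and disputes how much it matters.

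- **No strict impossibility.** The inclusion criterion describes a habitual pattern, while the exclusion concerns the actual interval, so a late patient can meet both. This is true, but such patients are not the on-schedule patients that Section 4 describes.
- **False precision at the 4-month end.** The protocol speaks in whole months, so a one-day shortfall should carry little weight. This stands: the 4-month endpoint is borderline. It does not touch the 3-month cycle, where the gap is about a month.
- **Carry-over may be small.** The opening paragraph of Experiment 2 puts the peak effect at about 3 weeks and its duration at 3 months, so the previous injection would be near the end of its stated effect at about 90 days. But the plan also expects a significant reduction at 3 months, so residual effect at baseline cannot be dismissed on its own terms.
- **Safeguards exist.** Patients must be MAS 2 or 3, the numbers of 2s and 3s are matched, treatment plans are to be balanced, the list of matching variables is open-ended, and baseline reflex torque is measured, so an imbalance would be visible. These limit the likely harm. None of them fixes time since injection or repairs the eligibility text.
- **Exploratory study, unquantified bias.** This is correct, and no bias is claimed. But the criterion decides who may enrol, and that does not depend on the size of any bias.

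**Conclusion.** The contradiction is real and must be fixed. Sections 4 and 5 cannot both be followed for an on-schedule 3-month patient, who is about 31 days short of the exclusion limit at baseline (29 to 32 by calendar). The same exclusion also covers nearly all of the inclusion range in its own list, and all of it if judged at screening.

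This rests on reading the exclusion as elapsed time since any last botulinum toxin injection, on routine injections given on schedule, and on screening taking place on the stated day. The documents give neither actual injection intervals nor a figure for residual effect at 90 versus 122 days. How many of the 16 patients would be affected, and by how much the results could shift, is therefore unknown.

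**What to change.** Amend Sections 4 and 5 so that the Experiment 2 population, the inclusion interval, the exclusion interval and the recruitment and baseline timing agree. State the day on which time since last injection is judged. Which interval applies, and which text changes, is a clinical decision for the sponsor.

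Separately, record days since last botulinum toxin injection at baseline for every Experiment 2 patient and compare it between the two groups. This is not needed to cure the contradiction, but it would make any imbalance between groups visible.

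The cost is a short amendment to the eligibility text and one extra data field. Any effect on recruitment depends on the sponsor's choice.

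### Experiment 2 forms its two groups of 8 only by efforts to match or balance during recruitment, with no random or concealed allocation described

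*Combined protocol and SAP*

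**What the plan says.** In section 4, Experiment 2, the Patient selection paragraph recruits 16 post-stroke patients who already receive regular BTX for their biceps "into two groups: the IZ-guided injection group and the standard injection group". It does not say how a patient comes to be in one group or the other. What the protocol does say about forming the groups is spread over four places:

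- Section 4, BTX injections: "The number of MAS (2s or 3s) will be matched between two groups".
- Section 4, Pitfalls for Experiment 2: "Efforts will be made to balance treatment plans between groups in the recruitment process".
- Section 5, before the eligibility criteria: "Gender will be balanced".
- Section 5, after the exclusion criteria: "Efforts will be made to match a variety of measures between two groups, such as age, gender, time from stroke". Spasticity in other elbow flexors and injection sites are given as further examples. The protocol then adds: "Given the volume of patients in TIRR Spasticity Management Clinic, we are confident that we can achieve this goal".

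The named analysis, in sections 4 and 6, is a two-way ANOVA of reflex torque with GROUP (2 levels) and TIME (3 levels). No covariate or matched-pair term is mentioned. Both sections predict a significantly larger reduction in the guided group.

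**The concern.** Matching during recruitment acts only on the factors that someone chooses to match. It leaves open who enters which group on everything else, and here the choice can be made by people who know both the patient and the vacant place. Every candidate is a repeat recipient ("receiving repeated botulinum toxin injection every 3-4 months") and comes from the clinic that treats them, so clinic staff could plausibly know how a patient responded to earlier injections. That is one example of a factor linked to response that the protocol does not name for matching.

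If such a factor differs between groups, a difference in torque reduction is partly a difference in patients. Recorded imbalance can be partly adjusted for afterwards; unrecorded selection cannot. At stake is how to read the comparison for which Experiment 2 is set up.

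**Working it through.** **Check of the text.** I read the whole protocol for any random sequence, minimisation, allocation list, concealment, or named person who assigns patients, and found none. Consent and title pages were removed from the supplied text, but the design, human-subjects and analysis sections, where allocation would be described, are present. The protocol never calls Experiment 2 randomised, so this is an absent safeguard and not a contradiction.

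**Illustration of the size.** The protocol gives no SD, effect size or significance level, so there is no figure of its own to reproduce on this point. Inputs:

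- n = 8 per group (section 4, Limitation; section 5).
- Two-sided 5% level: assumed.
- True guidance effect: zero, assumed.
- Selection-driven group difference d in change in reflex torque: 0.3, 0.5 or 0.8 SD of change, assumed.

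*Two-sample t-test on change.* The df are 2 × 8 − 2 = 14, the critical value is 2.145, and the noncentrality is d × √(n/2) = 2d.

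*GROUP by TIME interaction.* This assumes a repeated-measures ANOVA with compound symmetry and the same shift at 3 weeks and 3 months. The plan does not state this error structure. The df are 2 and (16 − 2) × 2 = 28, the critical F is 3.34, and the noncentrality is (n/2) × (2/3) × 2d² = 5.33d².

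| d (SD of change) | t noncentrality | t-test rejects | F noncentrality | Interaction rejects |
|---|---|---|---|---|
| 0.3 | 0.6 | 8.7% | 0.48 | 8.4% |
| 0.5 | 1.0 | 15.4% | 1.33 | 15.1% |
| 0.8 | 1.6 | 32.0% | 3.41 | 32.8% |

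The nominal rate is 5%. A stable difference in torque level between groups would leave the interaction at 5%, but it would enter the GROUP main effect. The plan does not say which term decides.

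**What random allocation leaves behind.** With 8 per group, the difference in means of a factor left unbalanced has standard error √(1/8 + 1/8) = 0.5 SD. It therefore reaches 0.5 SD or more in about 32% of randomised trials. The test's error rate already allows for chance imbalance of this kind; it does not allow for selection.

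**Balance on the sponsor's own factors.** I simulated 16 patients, with prevalence of MAS 3 and of other-flexor injection each assumed to be 50% (results for 30% in brackets). The table gives the chance that the two groups' counts differ by 3 or more.

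| Method | MAS 3 | Other-flexor injection |
|---|---|---|
| Random list fixed at 8:8 | 21% (17%) | 21% (17%) |
| Permuted blocks of 4 within MAS | 0% (0%) | 23% (18%) |
| Minimisation on both factors and group size, probability 0.8 of the better-balancing arm | 8% (6%) | 8% (6%) |

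Random allocation can therefore keep the balance on MAS that the sponsor wants.

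**The case against.** Much is controlled already. Product, amount and dilution are to be consistent between groups, both groups receive standard physical therapy, and the number of sites is fixed: "To standardize the procedure, we will choose 2 sites for all patients". The matched characteristics are sensible, and the list in section 5 is open, so prior response could be among them. The aim is stated as feasibility, the project is called exploratory, and a later study is foreseen. Sixteen randomised patients would still be unevenly matched on some factors. All of this stands, and it limits the severity. It does not remove the point, because the plan still predicts a significant between-group difference and offers no protection against selection on what is not matched.

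A reader might infer more than the documents support:

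- *That patients will be steered by earlier response, or that the result will favour guidance.* No section says who assigns patients or on what basis, and the direction of any bias is unknown.
- *That the percentages above describe this trial.* They follow from assumed shifts.
- *That selection would visibly distort the sample size of the future study, through the power analysis planned at completion.* A 0.5 SD bias is only one standard error at 8 per group, so swings as large would arise by chance under perfect randomisation.
- *That the ANOVA is the only between-group comparison.* It is the only named test; section 4 also plans to compare clinical assessments, including MAS, between groups.
- *That mapping on the baseline day contaminates baseline torque.* Section 4 puts the baseline assessment and the guided group's mapping on the day before injection without giving their order, but no such effect is documented.

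**Conclusion.** The concern holds as an omission in the design. A significant difference in Experiment 2 could not be attributed to guidance alone, and a null result could hide a benefit. For assumed shifts of 0.3 to 0.8 SD of change, the false-positive rate would be about 9% to 32% instead of 5%; the interaction figures also assume a repeated-measures ANOVA with compound symmetry. The actual bias could be nil. Because the work is exploratory and much of the treatment is standardised, this should be fixed but does not invalidate the project. Confidence in the textual finding is high.

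**What to change.** After consent, baseline MAS and reflex torque, and a record of the treatment plan for other elbow flexors, and before the guided-only 3DIZ session, allocate 1:1 by a concealed computer-generated random method that keeps balance on MAS (2 versus 3). Either of two methods would serve:

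- small permuted blocks within MAS strata, which is simpler but does not balance other-flexor injection; or
- minimisation with a random element (for example, probability 0.8 of the better-balancing arm) on MAS, other-flexor injection and group size.

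The sequence or program should be held by someone outside recruitment, such as the biostatisticians that section 4 says are available. Enter the balancing factor or factors, each with its TIME interaction, in the ANOVA, and state its error structure. Allocating at this point also settles the order of baseline and mapping.

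Costs: one allocation program; the total stays 16. The downsides are:

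- Less hand-matching on the remaining characteristics, as quantified above.
- The mapping team must stand by on each patient's baseline day, and about 8 of the 16 standbys go unused.
- Group sizes may not be exactly 8:8. In the minimisation simulation they were 8:8 in 68–69% of runs, 7:9 in 29–30%, and more unequal in about 2%.
- A few error df. If the ANOVA is repeated-measures and two factors are added, the interaction df fall from 28 to (16 − 2 − 2) × 2 = 24, and the critical F rises from 3.34 to 3.40.
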